- The interval between Visit 1 and Visit 4 can be accomplished in less than 6 weeks and will not be considered as a protocol deviation. If the ABPM needs to be repeated at Visit 3 (per criteria specified in Section 4.1.2.3), then the screening period may exceed 6 weeks and this will not be considered a protocol deviation.
- Participants who do not qualify for the MRI should move from Visit 1 to Visit 3.
- The visit date is determined in relation to the date of Visit 4 (randomization).
- Participants who are unable or unwilling to continue the study drug for any reason will perform an ED visit. If the participant is discontinuing during an unscheduled visit or a scheduled visit, that visit should be performed as an ED visit.
- Visit 99 is only applicable to participants who discontinue the double-blind study treatment prematurely and decline to complete the remaining scheduled study visits. If the participant is unwilling to complete all the study visits, then the participant should be encouraged to come back for a Visit 99, 48 weeks \pm 7 days after randomization, primarily for body weight measurement and assessment of adverse events. If the participant is unwilling to attend Visit 99, it should be documented in the participant medical record that the participant has refused to attend.
- Visit 801 (safety follow-up visit) should be performed 4 weeks after the last visit during the study treatment period or Visit 99.

Pharmacokinetic Schedule of Events

Sample #	Week Relative to Randomization	Collection Timepoint Relative to LY3437943 Weekly Dose
1	0	Predose (up to -8 hours)*
2	1	1 to 24 hours postdose
3	4	Predose (up to -8 hours)*
4	8	24 to 72 hours postdose
5	12	Predose (up to -8 hours)*
6	16	72 to 168 hours postdose
7	20	Any time during this week
8	24	Predose (up to -8 hours)*
9	36	Any time during this week
10	48	Postdose (approximately 1 week)*
11	Safety follow-up	5 weeks post last dose
12	Early discontinuation	Any time

* Immunogenicity (ADA) samples collected with PK at these visits.

2. Introduction

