ABPM will be repeated at Week 24 (Visit 11) and Week 36 (Visit 14) as described in Section 4.1.2.3. Study drug and injection supplies will be returned per the SoA (Section 1.3) and according to local requirements. New supplies will be dispensed as needed. Study site personnel will review the study drug preparation and injection technique using a vial and syringe at each office visit. Participants should be instructed to contact the investigative site for assistance as soon as possible if they experience any difficulties administering their study drug. Additional unscheduled visits may be scheduled if the participant needs additional support for the study drug injection technique.

Participants should also be advised about the appropriate course of action if study drug is not taken at the required time (for details on late/missing doses, see Sections 6.1 and 6.6). Study participants will be permitted to use concomitant medications that they require during the study, except certain excluded medications (see Section 6.5) that may interfere with the assessment of efficacy and safety characteristics of the study treatments.

Early Discontinuation of Treatment Visit

Participants unable or unwilling to continue the study treatment for any reason will perform an early discontinuation of treatment (ED) visit. If the participant is discontinuing during an unscheduled visit or a scheduled visit, that visit should be performed as an ED visit. A study participant who discontinues study drug permanently should be encouraged to continue in the study and to complete all study visits, including Visit 801 (See Participant Disposition and Timing of Safety Follow-Up figure below). Procedures should be completed according to the SoA (Section 1.3). When collected, patient-reported outcomes questionnaires should be administered as early as possible in the visit. Preferred administration order is

1. Patient Global Impression of Status for Physical Activity
2. SF-36v2 acute form, and
3. Eating Inventory.

Mental health questionnaires (PHQ-9, C-SSRS, and Self-Harm Form) should be completed after the assessment for AEs.

Visit 99

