The primary estimand (a precise definition of the treatment effect to be estimated) of interest in comparing efficacy of LY3437943 doses with placebo is the “efficacy estimand” (Section 1.1). The primary efficacy assessment, guided by the “efficacy estimand” will be conducted using the EAS (Section 3). A restricted maximum likelihood-based, dose-pooling, MMRM analysis will be used to analyze continuous longitudinal variables. All the longitudinal observations at each scheduled postbaseline visit will be included in the analysis. This dose-pooling variant of MMRM replaced the fixed effect of treatment group with that of the preplanned time-varying treatment doses at each time point in an effort to derive a more efficient estimator when the same treatment regimen over time is shared across the treatment groups due to preplanned titration (Qu et al. 2021). For example, in LY 4.0 mg (2.0 mg) and LY 8.0 mg (2.0 mg) arms, the doses administered for the first 4 weeks are both 2.0 mg. Therefore, pooling all the patients in these 2 groups provides a more efficient estimation in the effect of 2.0 mg which is also anticipated to increase the estimation precision for the later administered doses. The model for the analysis of the primary efficacy endpoint of percent change from baseline in body weight will include the fixed effects of treatment doses planned in the titration scheme: placebo, LY 1.0 mg, LY 2.0 mg, LY 4.0 mg (2.0 mg), LY 4.0 mg (4.0 mg), LY 8.0 mg (2.0 mg), LY 8.0 mg (4.0 mg), and LY 12.0 mg (2.0 mg), stratification factors including gender (males, females) and baseline BMI stratum (less than 36, greater than or equal to 36), and continuous, fixed covariate of baseline value, all nested within visits. An unstructured covariance structure will be used to model the within-participant errors. Significance tests will be based on LS means and robust ‘Huber-

White" standard errors. If this analysis fails to converge, the following covariance structures will be tested in order:

- autoregressive, and compound symmetry. The first covariance structure that converges will be used.

Unless specified otherwise, safety assessments will be guided by an estimand comparing safety of LY3437943 doses with placebo irrespective of adherence to study drug. Thus, safety analyses will be conducted using the SS.

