4.3. Primary Endpoint Analysis

The primary efficacy assessment, guided by the “efficacy estimand”, will be conducted using the EAS. For the “efficacy estimand”, the hypothetical strategy is used to handle the ICE (permanent discontinuation of study drug), so only data collected before the occurrence of any such ICEs will be used in the MMRM estimation (Section 4.1). Through the MMRM, the potential efficacy measures (after the ICEs) had participants not experienced ICEs will be implicitly imputed. To confirm efficacy of LY3437943 with adequate statistical power, the evaluation of the efficacy and safety endpoints for LY 4.0 mg and LY 8.0 mg compared with placebo will be made by pooling 2 dose escalation regimens, ie, combine LY 4.0 mg (2.0 mg) and LY 4.0 mg (4.0 mg) as LY 4.0 mg (pooled), and combine LY 8.0 mg (2.0 mg) and LY 8.0 mg (4.0 mg) as LY 8.0 mg (pooled). The primary efficacy comparison will be based on the contrast between each treatment group of LY3437943 and placebo at Week 24 (Visit 13) from the MMRM analysis of percent change from baseline in body weight using the EAS (Section 4.1). The analysis model and selection of covariance structure is described in Section 4.1. Treatment comparisons will be performed for the primary objective at the full significance level of 0.05.

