4.3.1. Definition of Endpoint

The primary efficacy measure will be percent change in body weight from baseline (Week 0) to Week 24. The percent change in body weight at each nominal visit is defined as:

$$\frac{(\text{post baseline body weight [kg]} - \text{baseline body weight [kg]})}{\text{baseline body weight [kg]}} * 100\%.$$

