4.6.1. Extent of Exposure

Listing of exposure to LY3437943 and placebo will be provided by treatment group using data from the SS. Summary of duration of follow-up (defined as time in days from date of randomization to the date of the last study visit) and/or duration on study treatment (defined as time in days from date of first dose of study treatment to date of last dose of study treatment plus 7 days) will be provided by treatment group using data from SS, in the following period:

- 48 weeks plus safety follow-up (Visit 801) for all randomized participants

For the summary of duration on study treatment, the frequency and percentage of participants falling into the following range will be summarized by planned treatment group as well:

- greater than 0
- 4 weeks or longer
- 8 weeks or longer
- 12 weeks or longer
- 16 weeks or longer
- 20 weeks or longer
- 24 weeks or longer
- 28 weeks or longer
- 32 weeks or longer
- 36 weeks or longer
- 40 weeks or longer
- 44 weeks or longer, and
- 48 weeks or longer.

In addition, the frequency and percentages of participants falling into the following study treatment exposure ranges may be summarized by planned treatment group:

- 0 weeks,
- longer than 0 weeks to less than 4 weeks
- 4 weeks or longer to less than 8 weeks
- 8 weeks or longer to less than 16 weeks
- 16 weeks or longer to less than 20 weeks
- 20 weeks or longer to less than 24 weeks
- 24 weeks or longer to less than 28 weeks
- 28 weeks or longer to less than 32 weeks
- 32 weeks or longer to less than 36 weeks
- 36 weeks or longer to less than 40 weeks
- 40 weeks or longer to less than 44 weeks, and
- 44 weeks or longer to less than 48 weeks.

No p-values will be reported in these summaries as they are intended to describe the study populations rather than test hypotheses about them.

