4.6.4. Vital Signs

In the case that multiple records of an individual vital sign are collected at the same visit, they will be averaged prior to being used for data summaries and analyses.

Descriptive summaries by treatment and by nominal visit will be provided for baseline and postbaseline values as well as change from baseline values.

Treatment differences in mean change will be analyzed using the MMRM model as described in Section 4.1 with all available data in the safety analysis set.

Counts and percentages of participants with treatment-emergent abnormal sitting systolic blood pressure, sitting diastolic, and pulse will be presented by treatment for participants who have both baseline and at least 1 postbaseline result. A treatment-emergent high result is defined as a change from a value less than or equal to the high limit at baseline to a value greater than the high limit at any time that meets the specified change criteria during the postbaseline period. A treatment-emergent low result is defined as a change from a value greater than or equal to the low limit at baseline to a value less than the low limit at any time that meets the specified change criteria during the postbaseline period. To assess decreases, change from the minimum value during the baseline period to the minimum value during the postbaseline period will be used. To assess increases, changes from the maximum value during the baseline period to the maximum value during the postbaseline period will be used. Both planned and unplanned measurements will be included in the analysis. The criteria for identifying patients with treatment-emergent vital sign abnormalities are stated in [Table GZBF.4.6](#).

Table GZBF.4.6. Categorical Criteria for Abnormal Treatment-Emergent Blood Pressure and Pulse Measurements

Parameter	Low	High
Systolic BP (mm Hg) (Supine or sitting – forearm at heart level)	≤ 90 and decrease from baseline ≥ 20	≥ 129 and increase from baseline ≥ 20
Diastolic BP (mm Hg) (Supine or sitting – forearm at heart level)	≤ 50 and decrease from baseline ≥ 10	≥ 90 and increase from baseline ≥ 10
Pulse (bpm) (Supine or sitting)	< 50 and decrease from baseline ≥ 15	> 100 and increase from baseline ≥ 15

Abbreviations: BP = blood pressure; bpm = beats per minute

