4.6.5. Electrocardiograms

Summary statistics by treatment and by nominal visit will be provided for ECG parameters (heart rate, PR, QRS, RR, and QT corrected using QTcF). When the QRS is prolonged (eg, a complete bundle branch block), QTcF should be used to assess ventricular repolarization. Thus, for a particular ECG, the following will be set to missing (for analysis purposes) when QRS is 120 msec or longer: QT and QTcF. Change from baseline to postbaseline values for ECG parameters will be summarized for patients who have both a baseline and at least 1 postbaseline result. Only planned measurements will be included in the mean change analyses. The criteria for identifying participants with treatment-emergent quantitative ECG abnormalities is based on [Table GZBF.4.7](#). The counts and percentages of participants who meet following criteria at any time during the entire study period (including the off drug follow up time period) will be summarized by treatment group:

- treatment-emergent ECG abnormalities as listed in [Table GZBF.4.7](#)
- PR greater than or equal to 220 msec with 0% through 25% and higher than 25% increase from baseline
- QTcF greater than 500 msec, and
- treatment-emergent increase from baseline in QTcF interval of greater than 30 msec, 60 msec, or 75 msec.

Treatment-emergent qualitative ECG abnormalities are defined as qualitative abnormalities that first occurred after baseline. A listing of abnormal qualitative ECGs will be created (see).

Table GZBF.4.7. Selected Categorical Limits for ECG Data

Parameter	Low		High	
	Males	Females	Males	Females
Heart Rate (bpm)	<50 and decrease ≥ 15	<50 and decrease ≥ 15	>100 and increase ≥ 15	>100 and increase ≥ 15
PR Interval (msec)	<120	<120	≥ 220	≥ 220
QRS Interval (msec)	<60	<60	≥ 120	≥ 120
RR Interval (msec)	<300	<300	>1714	>1714
QTcF (msec)	<330	<340	>450	>470

Abbreviations: bpm = beats per minute; ECG = electrocardiogram; QTcF = Fridericia's corrected QT interval.

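### Does the primary MMRM lose the body weight taken when a participant stops study drug?

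*SAP*

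**What the plan says.** SAP 4.1 General Considerations fits the primary MMRM with all effects nested within visit and an unstructured covariance, and states: "All the longitudinal observations at each scheduled postbaseline visit will be included in the analysis". SAP 4.3.1 defines the endpoint by nominal visit: "The percent change in body weight at each nominal visit is defined as" the change from baseline divided by baseline weight.

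For the efficacy estimand, permanent discontinuation of study drug is the only intercurrent event (ICE). It is handled hypothetically, "so only data collected before the occurrence of any such ICEs will be used in the MMRM estimation" (SAP 4.3). The Efficacy Analysis Set in SAP 3 likewise leaves out what is recorded once study drug has been stopped. Neither place dates the event relative to the last weekly dose. For exposure, SAP 4.6.1 does give a convention: "time in days from date of first dose of study treatment to date of last dose of study treatment plus 7 days".

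Protocol 4.1.1.1 says of the stopping visit: "If the participant is discontinuing during an unscheduled visit or a scheduled visit, that visit should be performed as an ED visit". The Schedule of Activities (Protocol 1.3) collects weight at ED and gives that column no week. Up to Week 24, weight is scheduled at Weeks 0, 1, 4, 8, 12, 16, 20 and 24.

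**The concern.** An unstructured MMRM needs every observation in a visit slot, and the SAP text never mentions the ED visit. If an ED weight has no slot, the model discards the last measurement before stopping and imputes onward from an older one. For a participant who stops at the Week 24 visit, the discarded value would be the primary endpoint itself.

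The imputation assumes data missing at random given the retained weights. If people stop because of how they are doing at that moment, and do so differently by arm, dropping the ED weight breaks that assumption. The effect would look too small if poor responders leave placebo or fast losers leave active drug, and too large if poor responders leave active drug. The estimates feed Phase 3 dose selection, and two analysts could program the same SAP differently.

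The SAP also appears to handle this question elsewhere. For vital signs it says "Both planned and unplanned measurements will be included in the analysis", and for ECGs "Only planned measurements will be included in the mean change analyses". It has no such sentence for body weight.

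**Working it through.** **1. The plan's own figure.** Inputs from Protocol 9.2 and SAP 5: 300 randomized, two tenths to each dose level and to placebo, 20% dropout, SD 10, difference 8, two-sided 0.05.

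- Randomized per group: 300 × 2/10 = 60. Completers: 60 × 0.8 = 48.
- SE of a difference: 10 × √(2/48) = 2.04. Ratio: 8/2.04 = 3.92.
- Power: Φ(3.92 − 1.96) = 0.975 (normal), or 0.972 (noncentral t). The stated 97% or more is reproduced.

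**2. The text, case by case.**

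- *Stopping at a scheduled visit.* Protocol 4.1.1.1 still describes this as a scheduled visit, performed with ED procedures. SAP 4.1 takes all observations at scheduled postbaseline visits. The weight can therefore be read as included, and this covers the participant who stops at Week 24.
- *Stopping on an unscheduled date.* No slot exists and the weight stays out. That matches the ECG sentence, which limits mean change to planned measurements. The vital-signs sentence is no counterexample. It belongs to the paragraph on categorical treatment-emergent abnormalities, and mean change in vital signs uses the same Section 4.1 MMRM with no extra visit rule.
- *Before or after the ICE?* SAP 4.6.1 counts treatment to 7 days after the last dose. The Week 24 PK sample is predose on a weekly regimen, so a continuing participant's weight at that visit is also about a week after the previous dose. The Week 48 visit is about a week after the final dose. Treating an ED weight within 7 days of the last dose as on-drug fits both.

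**3. Size if every ED weight were dropped.** This is the worst reading. The documents give no stopping model, so the ranges rest on assumptions. Bias is measured on active minus placebo (true value −8); positive means the effect is understated.

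*Settings A:* 120,000 simulated participants per arm, maximum likelihood for an MMRM with a common unstructured covariance, 4-week correlation 0.85 to 0.95, stopping odds ratio 1.5 to 2.2 per SD of current weight change, 20% stopping unless shown.

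| Stopping pattern | Bias, points |
|---|---|
| Unrelated to weight; or depends only on the previous retained weight; or same mechanism and rate in both arms | 0.03 or less |
| Same mechanism, 10% against 25% stopping | −0.07 to −0.26 |
| Weight-related in one arm only | 0.06 to 0.34, either sign |
| Opposite mechanisms in the two arms | +0.15 to +0.64 |
| Opposite mechanisms, 10% stopping | +0.08 to +0.32 |

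*Settings B:* 100,000 per arm, odds ratios 2 to 4 (inverted in the active arm for opposite mechanisms), a different trajectory and correlation. At 20% stopping the largest shifts are −7.99 to −7.44 (0.55) with weight-related stopping in placebo only, and −7.97 to −6.86 (1.11) with opposite mechanisms. At 30% they are 0.80 and 1.67. If stopping depends only on the last scheduled weight, the shift is 0.04 or less, within simulation error.

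**4. Against the standard error.**

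- One arm, settings A: 0.34/2.04 = 0.17 SE. Coverage of a 95% interval: Φ(1.79) − Φ(−2.13) = 0.947.
- Opposite, settings A: 0.64/2.04 = 0.31 SE. Coverage: Φ(1.65) − Φ(−2.27) = 0.939.
- Opposite, settings B, 20%: 1.11/2.04 = 0.54 SE. Coverage: Φ(1.42) − Φ(−2.50) = 0.916. Power at a difference of 6.9 is about 92%.

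**5. What an added rule would gain.** Moving every ED weight to the next visit is not neutral. In settings B with stopping unrelated to weight, it moved −8.05 to −7.87, an error of 0.18 where there had been none. With stopping driven by the last scheduled weight it moved −7.93 to −7.41. A narrower rule, using the protocol's visit windows, left 0.09 or less, against 0.08 to 0.48 with ED weights dropped. It used 56 to 83% of ED weights when 50 to 80% of stops were assumed to fall at scheduled visits. Most of what it keeps is therefore weight that SAP 4.1 already admits.

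**The case for a change.** The best case for a change is that the SAP is silent. The ED visit is not mentioned, the ICE is not dated, and a stopping visit held on schedule may be labelled ED in the database, so a programmer filtering on nominal visit could lose it. Section 4.3 also ties Week 24 to Visit 13, whereas the schedule has Week 24 at Visit 11 and Visit 13 as a Week 32 telephone visit. Keeping ED weights brings the bias close to zero in settings A (0.03 or less), and a sentence costs little.

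The silence is real, and so is the slip in the visit number, but Section 4.3 names the week as well, so nobody would analyse a telephone visit that has no weight. The argument from size is weaker. A material shift needs stopping to depend on the weight at that moment beyond one measured at most 4 weeks earlier, and to differ by arm in mechanism or rate. The documents support neither. The 20% is dropout from completing the study, not drug stopping by Week 24.

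Harm to dose selection was not shown. The simulations had two arms, without dose pooling, strata or a baseline covariate. Bias arising in placebo is common to every dose contrast and leaves the differences between doses unchanged. Different stopping patterns between active arms could move doses relative to each other, and that was not examined. After Week 24, weights are 12 weeks apart (Weeks 24, 36, 48), so the same silence could matter more for the secondary Week 48 endpoint. That was not quantified either.

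**Conclusion.** No change follows. The plan leaves a visit-assignment detail unwritten, and its own wording leads an analyst to a sensible answer: use the weight when the stopping visit is a scheduled visit and the last dose is recent, and leave it out when it has no visit slot. On that reading the feared loss of a Week 24 value does not arise, and what is lost from unscheduled stops is less than the figures above, which drop every ED weight. With opposite mechanisms, odds ratio 1.8 and correlation 0.85, for example, keeping half of the ED weights cut the bias from 0.50 to 0.25 point.

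Dropping all of them costs 0.03 point or less in the unremarkable cases and 0.06 to 0.34 point with weight-related stopping in one arm, against an SE of 2.04. Only strong and opposite stopping in the two arms reaches about 1.1 points at 20% stopping, or 1.7 at 30%. The superiority conclusion stands under the planning assumptions. The sizes depend on assumed correlations, odds ratios and stopping rates that the documents do not give.

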4.5.2. Bayesian Analyses for Dose-Response

The longitudinal dose-response model as proposed by Qu et al. (2019) will be adapted here. This model also considers the preplanned dose changes that occur during the titration period. Let $\theta = (\theta_1, \theta_2, \dots, \theta_m)$ be the doses a participant has planned to take and $t_c = (t_{c1}, t_{c2}, \dots, t_{cm})$ be the corresponding times when the dose changes where t_{ci} indicates the time for dose to change from θ_i to θ_{i+1} . Therefore, the mean function of the parameter of interest at time t is modelled by:

$$f_{\theta, t_c}(t) = f(t; \theta_1) + \sum_{i=1}^{m-1} [f(t - t_{ci}; \theta_{i+1}) - f(t - t_{ci}; \theta_i)]I(t > t_{ci}),$$

where $I(X)$ is the indicator function that takes value 1 when the condition X holds. The $f(t; \theta)$ is defined such that

$$f(t; \theta) = \frac{\lambda(\theta)(1 - e^{-k(\theta)t})}{1 - e^{-k(\theta)d}},$$

where d is the maximum duration of the treatment period in weeks ($d = 24$ for primary analyses while $d = 36$ for final analysis), $\lambda(\theta)$ is the dose-response function for the maximum response at dose θ and $k(\theta)$ is dose θ 's rate parameter. This formulation of the mean function $f(t; \theta)$ was introduced by Fu and Manner (2010) to characterize the change from baseline over time in a continuous outcome that could be approximated with a pattern of exponential decay. It assumes a monotone time profile with the maximum effect reached at time d . The longitudinal data $Y_{\theta, t_c, jt}$ for participant j at time t with titration scheme (θ, t_c) will be fitted by adding the error terms to the mean function $f_{\theta, t_c}(t)$ where

$$Y_{\theta, t_c, jt} = f_{\theta, t_c}(t) + \frac{s_j(1 - e^{-k(\theta_1)t})}{1 - e^{-k(\theta_1)d}} + \epsilon_{jt},$$

$s_j \sim N(0, \sigma_s^2)$ and $\epsilon_{jt} \sim N(0, \sigma^2)$ are independent, denoting between-subject variation and within-subject variation respectively. Given s_j , $Y_{\theta, t_c, jt} \sim N(f_{\theta, t_c}(t) + \frac{s_j(1 - e^{-k(\theta_1)t})}{(1 - e^{-k(\theta_1)d})}, \sigma^2)$.

For characterizing the body weight change, we use a different formulation of $f_{\theta, t_c}(t)$ that showed better fitting in the analyses of historical trials and simulation studies while keeping all other elements unchanged. In the new formulation,

$$f_{\theta, t_c}(t) = f(t; \theta_1) + \sum_{i=1}^{m-1} h(t - t_{ci})[f(t; \theta_{i+1}) - f(t; \theta_i)]I(t > t_{ci}),$$

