4.7.2. Subgroup analyses

Subgroup analyses of the primary endpoint will be made to assess consistency of the intervention effect across the following subgroups:

- age group: younger than 65 versus 65 years or older
- race
- sex: female versus male
- ethnicity
- BMI (kg/m^2) group: less than 30 versus greater than or equal to 30 and less than 35 versus greater than or equal to 35 and less than 40 versus greater than or equal to 40, and
- baseline BMI (the minimum or greater to less than the first quartile, the first quartile or greater to less than the median, the median or greater to less than the third quartile, the third quartile or greater to the maximum).

For each subgroup analysis, MMRM model as described in Section 4.3.2 will be used.

If the number of participants is too small (less than 10%) within a subgroup, then the subgroup categories may be redefined prior to unblinding the study. Additional subgroup analyses may also be performed.

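### If the unstructured model fails, the SAP drops straight to covariance forms that usually assume constant variance; a minor point with a one-sentence fix

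*SAP*

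**What the plan says.** SAP 4.1 sets the starting point: "An unstructured covariance structure will be used to model the within-participant errors". If that model does not converge, the alternatives tried in order are "autoregressive, and compound symmetry. The first covariance structure that converges will be used". The SAP does not say whether these have common or visit-specific variances. Inference is also fixed there: "Significance tests will be based on LS means and robust" Huber-White standard errors.

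SAP 4.3 handles permanent discontinuation of study drug by the hypothetical strategy, "so only data collected before the occurrence of any such ICEs will be used in the MMRM estimation". It adds: "Through the MMRM, the potential efficacy measures (after the ICEs) had participants not experienced ICEs will be implicitly imputed".

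SAP 4.5.2, the Bayesian dose-response model, gives weight change a participant-level term that grows with time and an independent error of constant variance, "denoting between-subject variation and within-subject variation respectively". For body weight a different mean function is adopted because it showed "better fitting in the analyses of historical trials and simulation studies while keeping all other elements unchanged". The variance structure is therefore kept for weight.

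SAP 4.7.2 carries the same model into the subgroups: "For each subgroup analysis, MMRM model as described in Section 4.3.2 will be used".

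**The concern.** Under the hypothetical strategy, the Week 24 mean in each arm includes model-based predictions for participants who have stopped study drug. Those predictions run through the fitted covariance. If it is wrong, the predictions are wrong, and under response-dependent dropout the arm means are biased. A sandwich standard error corrects the stated precision; it does not move the estimate.

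The SAP's fallback goes from the most flexible structure to two of the most restrictive, and in their usual form these contradict the variance pattern that the SAP itself assumes for weight. At stake are the estimate and its interval coverage in any fit where the fallback is used.

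**Working it through.** **Inputs from the documents.** Week 24 SD 10%, difference -8, 20% dropout, 48 completers per dose and placebo, 2-sided 0.05 (SAP 5). Fasting weight after baseline at Weeks 1, 4, 8, 12, 16, 20, 24, 36 and 48 (Protocol 1.3). Variance form from SAP 4.5.2.

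**Assumptions not in the documents.** Rate k of 0.03 to 0.08 per week (0.05 in the tables); within-participant SD of 2 to 4 (2 in the tables); placebo change -2%; stopping drug depends on the last observed value with odds ratio 2 per SD; the 20% dropout applies to stopping study drug.

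**1. The plan's own figure.** SE = 10 × √(2/48) = 2.04. 8/2.04 - 1.96 = 1.96, so power is about 97.5% (97.25% with the noncentral t). This reproduces the stated 97%. The plan gives no figure for the fallback.

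**2. Variance implied by SAP 4.5.2.** Var(t) = σs² g(t)² + σ², with g(t) = (1 - e^(-kt))/(1 - e^(-24k)). With k = 0.05 and σ = 2, SD 10 at Week 24 gives σs² = 100 - 4 = 96.
- Week 1: g = 0.0488/0.6988 = 0.070; variance 96 × 0.0049 + 4 = 4.5; SD 2.1. With σ = 4, σs² = 84 and the SD is about 4.1.
- Week 8: g = 0.3297/0.6988 = 0.472; variance 96 × 0.2226 + 4 = 25.4; SD 5.0.
- Week 20: g = 0.6321/0.6988 = 0.905; variance 96 × 0.818 + 4 = 82.6; SD 9.1.

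The spread rises from about 2-4 to 10. Correlation with Week 24 rises from 96 × 0.070/(2.1 × 10) ≈ 0.32 at Week 1 to 96 × 0.905/(9.1 × 10) ≈ 0.96 at Week 20, so neither AR(1) nor compound symmetry has the right correlation shape either.

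**3. Effect on prediction.** For someone who stops after Week 8, the slope of Week 24 on the Week 8 value alone is 96 × 0.472/25.4 = 1.8. With constant variance that slope is a correlation and cannot exceed 1, so the deviation is carried forward too weakly.

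**4. Large-sample bias in the Week 24 contrast** (true value -8; 100,000 per arm; seven visits; 20% dropout in each arm unless stated; + means attenuation).

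| Dropout pattern | Unstr. | AR(1) | CS | ARH(1) | CSH | Het. Toeplitz |
|---|---|---|---|---|---|---|
| Same in both arms | -0.06 | -0.04 | -0.03 | -0.04 | -0.05 | -0.04 |
| Same dependence, 30% placebo, 10% active | -0.06 | +0.58 | +0.77 | +0.49 | +0.32 | +0.31 |
| Active non-responders leave | -0.06 | -0.63 | -0.82 | -0.55 | -0.41 | -0.38 |
| Opposite: placebo loses poor, active loses good responders | -0.06 | +1.12 | +1.50 | +0.96 | +0.66 | +0.62 |
| Opposite, decaying correlation | -0.06 | +1.00 | +1.42 | -0.11 | -0.30 | -0.11 |

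The first four rows use the SAP 4.5.2 covariance. The last keeps its SD profile with correlation that decays over time. The unstructured values are simulation noise. When dropout was unrelated to response, bias was about zero for every structure.

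Two other assumed profiles bracket these results. With SD about 3 at Week 1, the bias was 0.35-0.6 (one arm) and 0.7-1.2 (opposite). With nine visits and SD 1.2 to 12.5, it was 0.6 (AR) and 0.9 (CS) for one arm, and 1.2 and 1.7 for opposite. With odds ratio 3, opposite dependence gave up to 2.3.

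**5. At trial size** (five arms of 60, 400 replicates, opposite dependence, robust SEs).

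| | Bias | Robust SE / empirical SD | 95% CI coverage | Rejection at -8 | Rejection at 0 |
|---|---|---|---|---|---|
| Unstructured | -0.02 | 1.86 / 1.91 | 95.3% | 98.8% | 4.8% |
| AR(1) | +1.19 | 1.86 / 1.88 | 90.7% | 95.0% | 9.2% |
| CS | +1.55 | 1.87 / 1.87 | 88.0% | 92.2% | 12.0% |

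The robust SEs are right and coverage still falls, because the centre has moved. Monte Carlo error on coverage is about √(0.95 × 0.05/400) = 1.1 points.

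**6. Where the fallback could arise.** An unstructured matrix has 7 × 8/2 = 28 parameters to Week 24 and 9 × 10/2 = 45 to Week 48. With about 300 participants it was positive definite in all 1,600 simulated trials. Subgroups may be redefined below 10%, so the practical floor is about 30 people; a BMI quartile has about 75. The first interim has about 0.15 × 300 = 45. The simulations used monotone dropout, no stratification covariates and no dose pooling.

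**The case against.** The strongest reply is that this rule will rarely be used. Nothing in the documents shows that the unstructured model would fail. Even at 30 people, with seven arms, three covariates and 20% random monotone dropout, the unstructured matrix was identified in all 2,000 simulated data sets with seven visits and in 99.4% with nine. Identification does not guarantee software convergence, but a parameter count alone is not evidence of failure. This stands.

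Where failure is more plausible, noise dominates. A 30-person subgroup has about 30 × 0.2 × 0.8 = 4.8 completers per pooled dose, giving SE 10 × √(2/4.8) = 6.5. At 60 people the SE is 10 × √(2/9.6) = 4.6, so even a 1.7-point bias is 0.37 SE. This also stands. The order is pre-specified, too, and leaves the analyst no choice, which is a merit.

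Four stronger readings are tempting but not supported:
- A reader might infer that the SAP prescribes constant variance. It names no variance form; the fault is that it leaves the form open.
- A reader might infer that response-dependent dropout is enough to bias the contrast. The arm biases cancel when rate and dependence are the same in both arms.
- A reader might infer that the addendum is exposed. Its endpoints are assessed after baseline at Weeks 24 and 48 only (SAP 7.7), so an unstructured matrix has three parameters, and the addendum's primary analysis is ANHECOVA.
- A reader might blame the uneven visit spacing. The 12-week gaps come only after Week 24.

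What survives is that arm-differential dropout is foreseeable. Lack of efficacy is a listed discontinuation reason (SAP Table GZBF.4.1), and Protocol 7.1 and 6.6.2 provide for stopping drug at low BMI, which removes strong responders, though perhaps few.

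**Conclusion.** The point holds as a minor one. The fallback names no variance form, and the usual forms conflict with the SAP's own weight model. If it is invoked and dropout differs between arms in rate or in dependence on response, the Week 24 contrast is biased by roughly 0.4-0.9 points (one-arm dependence) or 0.7-1.7 points (opposite dependence), against an assumed -8. The bias can attenuate or exaggerate the effect, and robust standard errors do not remove it. These sizes rest on about 20% dropout, odds ratio 2 per SD in the tabulated runs, and the assumed covariance profiles; stronger dependence or heavier dropout gives more, and equal dropout gives about none.

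A reader might take the 9-12% rejection rates at zero effect as a threat to the primary conclusion. They apply only if the full-trial model falls back and the two arms lose opposite kinds of responder. The first is unlikely with 28 to 45 covariance parameters and about 300 participants. The practical exposure is in small subgroup fits and, if weight is analysed there, the first interim, where sampling error is also large.

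**What to change.** Replace the fallback sentence in SAP 4.1 with an ordered list:
1. Refit the unstructured model with other starting values or optimizer settings.
2. Heterogeneous Toeplitz.
3. Heterogeneous AR(1), then heterogeneous compound symmetry.
4. Only then the homogeneous forms.

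State the variance form of each, and report which structure was used in every fit. Keep the robust standard errors.

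The cost is one sentence and some covariance parameters. With nine visits, heterogeneous Toeplitz has 9 + 8 = 17 against 2 for AR(1) or compound symmetry, so 15 more; heterogeneous AR(1) and compound symmetry have 10 each, so 8 more. In the smallest fits these may also fail, and the list then moves on.

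The change reduces the bias rather than always removing it, because correlation shape matters as well as variance. Under the SAP 4.5.2 form with opposite dependence, heterogeneous Toeplitz cut AR(1)'s 1.12 to 0.62, while heterogeneous AR(1) cut it only to 0.96. The order within step 3 is not critical: heterogeneous compound symmetry did better under the SAP form (0.66 against 0.96), and heterogeneous AR(1) under decaying correlation (-0.11 against -0.30).
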